2.2 Analysis sets

The Full Analysis Set (FAS) comprises all subjects to whom study treatment has been assigned by randomization. According to the intent to treat principle, subjects will be analyzed according to the treatment and stratum they have been assigned to during the randomization procedure. Tabulations of demographic and baseline characteristics, disposition, and important protocol deviations (PD) will utilize FAS.

The Safety Set (SAF) includes all subjects who received at least one dose of study treatment. Subjects will be analyzed according to the study treatment received, where treatment received is defined as the randomized/assigned treatment if the subject took at least one dose of that treatment or the first treatment received if the randomized/assigned treatment was never received.

Screen failures will not be included in any analysis sets.

Please refer to [appendix 5.4](#) for Rules of exclusion criteria of analysis sets.

2.3 Subject disposition, demographics and other baseline characteristics.

2.3.1 Subject disposition

Subject disposition will be summarized on FAS. The number and percentage (based on the number of subjects within each randomized treatment arm) of subjects who completed / discontinued the study will be displayed by initially assigned treatment and overall. The primary reason for premature study discontinuation will be displayed by initially assigned treatment and overall. The core phase completers are defined as subjects who either complete week 52 on study or complete safety follow up visit.

Treatment completion will be summarized in the same manner as subject disposition. The number and proportion of subjects, who complete the study treatment or discontinue the study treatment prematurely along with the primary reason for study drug discontinuation will be presented.

Disposition and treatment completion data will also be presented in listings.

Screen Failures: The total number of subjects screened and the number of subjects screened, but not randomized (discontinued prior to screening or baseline phase completion) will be summarized, including the reason for screening failure. Data on screen failures will also be presented in listings.

Analysis sets: The number of subjects within each of the analysis sets used in the study will be summarized.

The impact of COVID-19 pandemic on study subjects with respect to randomization, study and treatment discontinuations, protocol deviations and dose interruptions will be assessed and summarized for pre- and during COVID-19 phases. The pandemic phase will be defined based on start date of pandemic. For Italy start date of pandemic will be used as 23Feb2020 and for rest of the world start date of pandemic will be used as 01March2020.

2.3.2 Protocol deviations

The number of subjects with PDs according to the applicable standard operating procedures (SOP-7035752 V4.0) will be presented. The results of the PDs will be grouped using the broad categories defined in the applicable SOP, which currently are:

- Eligibility: Subject did not satisfy entry criteria
- Withdrawal: Subject developed study/treatment withdrawal criteria during the study, but was not withdrawn
- Study Drug: Subject received the wrong treatment or incorrect dose
- Concomitant Medication: Subject took a prohibited concomitant medication
- Other GCP deviation

A complete list of the PDs can be found in the Edit Check Specifications document in CREDI. Subjects with PDs and PDs leading to data exclusion from analysis sets will be listed.

In addition to the pre-defined standard PD terms, Novartis has also defined 6 new protocol deviations and the corresponding relationship (health status related vs. site lockdown, patient concerns, etc.) to the COVID-19 pandemic in line with “FDA Guidance on Conduct of Clinical Trials of Medical Products during COVID-19 Public Health Emergency” (March 2020) and “Guidance on the management of clinical trials during the COVID-19 (coronavirus) pandemic” (April 2020) from EMA as listed below. The following deviations related to the COVID-19 pandemic will be summarized.

- Missing visits
- Changes in procedures and assessments
- Planned visits not done at sites
- Changes in drug supply method
- Treatment not given
- Patient discontinuation due to COVID-19 situation
- Other study specific PDs

A cross-tabulation of COVID-19 related PD vs. corresponding relationship will also be produced.

2.3.3 Demographic variables and other baseline characteristics

Demographic variables and other baseline characteristics including previous migraine treatments will be summarized for each initially assigned treatment group and for all subjects (total) using FAS.

At baseline (end of the baseline period; see [Section 2.1.1.4](#), baseline definition), the following demographic and baseline characteristics will be summarized:

- Categorical variables:
 - Age (< 65 years, \geq 65 years)
 - Sex
 - Ethnicity
 - Race
 - Acute headache medication (none, migraine-specific/non migraine-specific) during baseline phase
 - Strata: Prior prophylactic migraine medication treatment failure (due to insufficient efficacy or poor tolerability) reported during screening / baseline period: 1 treatment failure (TF1) vs 2 treatment failures (TF2)
 - Aura status during baseline: Migraine with aura (ever experienced a migraine with aura during the baseline period), migraine without aura (never experienced any migraine with aura during the baseline period)
- Continuous variables:
 - Age
 - Height (cm)
 - Weight (kg)
 - Body Mass Index (BMI, kg/m²)
 - Age at onset of migraine (years)
 - Disease duration of migraine with or without aura (years)
 - Monthly migraine days during baseline phase
 - Monthly migraine attacks during baseline phase
 - Monthly headache days during baseline phase
 - Monthly acute migraine-specific medication use in days during baseline phase
 - Monthly acute headache medication use in days during baseline phase

Descriptive statistics (mean, median, standard deviation, minimum, and maximum) will be presented for continuous variables for each initially assigned treatment group and for all subjects (total) using FAS. The number and percentage of subjects in each category will be presented for categorical variables for each treatment group and all subjects (total).

If multiple races have been reported for a subject, the subject will be categorized as multiple races.

Summary of prior migraine prophylactic treatment and reasons for discontinuation will be presented by treatment group.

Subject disease history characteristics (listed below) collected on the “Headache and Migraine Frequency History” CRF page will be listed by treatment:

- Age at onset of migraine (years)
- Disease duration of migraine with or without aura (years) – derived.
- Frequency of migraines over the past 3 months (average days per month subject had migraines)
- Frequency of headache (migraine and non-migraine) over the past 3 months (average days per month subject had headache)

The impact of COVID-19 pandemic on subject demographics will be assessed by summarizing data for subjects randomized in pre- and during- COVID-19 phases. The pandemic phase will be defined based on either start date of pandemic as a global cutoff or by region.

2.3.4 Medical history

Relevant medical history/current medical conditions present before signing the Informed consent will be recorded on the ‘Medical History’ CRF page.

Any condition entered will be coded using the latest version Medical Dictionary for Regulatory Activities (MedDRA) prior to database lock and summarized by primary system organ class (SOC) and preferred term (PT) for each initially assigned treatment group and for all participants (total) using FAS. The SOCs will be presented in alphabetical order. Preferred terms will be ordered within each SOC by decreasing order of frequency in the AMG334 arm.

2.4 Treatments (study treatment, rescue medication, concomitant therapies, compliance)

2.4.1 Study treatment / compliance

Exposure will be calculated for subjects in the SAF. Descriptive statistics will be produced to describe the exposure to initially assigned study drugs as well as for switched drugs.

A listing of dose administration with the initially assigned study treatments along with switched drugs will be provided.

The duration of exposure since first injection/dose will be summarized descriptively by study treatment.

Additionally, the number and percentage of subjects with dose change and reason for dose change will be summarized by treatment group.

Summary of subjects switching to oral prophylactics from initially assigned study treatment with reasons for switching will be presented.

2.4.2 Prior, concomitant and post therapies

The number and percentage of participants receiving prior/concomitant medications, and significant non-drug therapy in SAF population will be summarized by Anatomic Therapeutic Chemical classification [ATC] (coded by WHO), preferred term and by treatment group. Summary of concomitant medications will be provided by initially assigned and switched drugs separately. As per B3 format there will be one record for each CMTRT variable value and the newly created CMCLS variable in SDTM.CM contains only lowest ATC class.

Use of acute headache medication during the baseline phase and the treatment period will be summarized by category of medication for each treatment group.

Use of alternative migraine therapies during the baseline phase and the treatment period will be summarized by category of medication for each treatment group.

2.4.3 Prohibited treatment

Analysis of concomitant medications, procedures that are prohibited as per protocol (see [Protocol Section 6.2.2](#)) and given during the conduct of the study will be addressed by the currently planned outputs of the Protocol deviations.

No separate outputs will be produced related to prohibited medications.

2.5 Analysis of the primary objective

2.5.1 Primary endpoint

The primary aim of the study is to evaluate the effect of AMG334 vs oral cycling on the net benefit, a measure of sustained long-term benefit in these two treatment paradigms of migraine prophylactic agents.

The primary endpoint of the study is the proportion of subjects achieving net benefit, defined as completion of one year on the initially assigned treatment and achieving at least a 50% reduction from baseline in monthly migraine days in the last month (week 52).

Subjects who complete one year on the initially assigned treatment and achieve at least a 50% reduction from baseline in monthly migraine days in the last month (week 52) are considered as responders for the purpose of primary endpoint.

A subject will be considered as a non-responder if

- a subject does not complete one year on the initially assigned treatment or
- a subject does not achieve at least 50% reduction from baseline in monthly migraine days or
- does not satisfy both of the above conditions

Analysis of the primary endpoint will utilize the FAS. Subjects will be analyzed according to their initially assigned treatment group regardless of the actual treatment received during the study.

2.5.2 Statistical hypothesis, model, and method of analysis

The primary analyses will compare the proportion of subjects in FAS who achieve a net benefit (defined in previous section) between AMG334 vs oral cycling.

Below is the hypothesis to be tested for primary analysis:

Null hypothesis: In subjects with episodic migraine, the AMG334 treatment group has the same effect as oral prophylactics group, in terms of the net benefit i.e. net benefit odds ratio =1.

Alternative hypothesis: In subjects with episodic migraine, the AMG334 treatment group is different from oral prophylactics group, in terms of the net benefit i.e. net benefit odds ratio $\neq 1$.

Randomization will be stratified by prior prophylactic migraine medication treatment failure (due to insufficient efficacy or poor tolerability) reported during screening / baseline period: 1 treatment failure (TF1) vs 2 treatment failures (TF2).

A Cochran-Mantel-Haenszel (CMH) test stratified by number of previous treatment failures (1 vs. 2) will be used under a 2-sided significance level of 0.05 to evaluate the association between the net benefit rate and the treatment. The p-value of the test, and the estimated odds ratio between AMG334 and active comparator, as well as its 95% confidence interval, will also be reported.

2.5.3 Handling of missing values/censoring/discontinuations

Subjects with missing monthly migraine day data at week 52 of treatment, and subjects that discontinue initially assigned treatment prior to the week 52 visit will be imputed as non-responders (not achieving a net benefit).

2.5.4 Sensitivity / Supplementary analyses

For the primary endpoint sensitivity analyses under missing at random (MAR) assumption will be performed. Multiple imputation (MI) techniques applying MAR approach will be used to assess the impact of missing values on the interpretation of the results from primary analysis. Since primary endpoint is composite, missing data imputation can be used only when subject completes 52 weeks on initially assigned treatment and has missing MMD value at week 52. To assess impact of these missing values on interpretation of results will be analyzed using below given sensitivity analyses:

1.1 Sensitivity analysis I: This data will be multiply imputed using the MAR assumption. The analysis method remains same as primary endpoint analysis. The multiple imputation model will be based on similar subjects in the same treatment arm.

Points to note:

- Due to composite primary endpoint off-treatment data cannot be used for primary analysis.

If MMD data is available say up to week 36 then data will be imputed from week 40 till week 52.

Table 2-4 Summary of primary endpoint and analysis methods

Endpoint	Analysis	Imputation
The proportion of subjects achieving net benefit, defined as completion of one year on the initially assigned treatment and achieving at least a 50% reduction from baseline in monthly migraine days in the last month (week 52)	Primary analysis: A Cochran-Mantel-Haenszel (CMH) test stratified by number of previous treatment failures (1 vs. 2) will be used under a 2-sided significance level of 0.05 to evaluate the association between the net benefit rate and the treatment.	No imputation.
	Sensitivity analysis: A Cochran-Mantel-Haenszel (CMH) test stratified by number of previous treatment failures (1 vs. 2) will be used under a 2-sided significance level of 0.05 to evaluate the association between the net benefit rate and the treatment.	Missing MMD data will be imputed using multiple imputation under MAR assumption. The multiple imputation model will be build based on similar subjects in the same treatment arm.

Supplementary analysis to assess impact of COVID-19 pandemic:

The primary endpoint is composite and one component is the completion of intially assigned treatment for 52 weeks. The impact of COVID-19 pandemic will be assessed by following analysis:

- a) The summary of discontinuations for initially assigned treatment and last available switched treatment will be provided by due to COVID-19 and non-COVID-19 reasons.
- b) In light of COVID-19 pandemic and its potential impact on treatment effect, an important scientific question of interest to address is to estimate the treatment effect had COVID-19 pandemic not occurred.
 - The target population is defined by all subjects in the study who received at least one dose of study treatment.
 - The variable of interest is reduction in MMD from baseline to week 52 on initially assigned treatment.
 - The intercurrent event describes how events that may occur after randomization are considered when assessing the treatment effect

- Discontinuation of initially assigned treatment due to non COVID-19 related reason: Subjects who discontinue due to non COVID-19 related reasons prior to week 52 will be considered as non-responders.
- Discontinuation of initially assigned treatment due to COVID-19 related reason (hypothetical strategy): All MMD data up to discontinuation of initially assigned treatment will be used. Ignore all the MMD data after treatment discontinuation and impute MMD data till week 52 using missing at random approach (MAR). The discontinuation reason due to COVID-19 pandemic will be identified from the defined COVID-19 protocol deviations.
- The summary measure is the odds ratio between two treatment arms. It will be obtained by CMH test similar to primary endpoint analysis. A subject will be responder if subject has at least 50% reduction in MMD from baseline at week 52 and completed initially assigned treatment for one year; otherwise subject will be a non-responder.

c) Summary statistics will be provided for change from baseline in MMD for subjects with COVID-19 infection separate for before and after COVID-19 infection period. The information about whether subject has COVID-19 infection is collected on AE CRF.

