2.1.1.3 Study day

Study Day 1 is defined as the first dose date of study treatment during initially assigned treatment period. For subjects who are randomized but not dosed after randomization, the Study Day 1 is defined as the date of randomization. Also, for subjects who are randomized but not dosed during initially assigned treatment period and received dose in switched period, the Study Day 1 is defined as the date of randomization.

Study Day is defined as the number of days from Study Day 1.

- Before Study Day 1:

Study Day = (Date of Interest – Date of Study Day 1)

- On or after Study Day 1:

Study Day = (Date of Interest – Date of Study Day 1) + 1

Therefore the day prior to Study Day 1 is -1.

The study day will be displayed in the data listings.

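### The COVID-19 supplementary estimand is defined on dosed subjects rather than the FAS, so if any randomised subjects were never dosed, its contrast with the primary result mixes a population change with the pandemic handling

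*SAP*

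**What the plan says.** The SAP defines two analysis sets in section 2.2. One follows randomisation: "The Full Analysis Set (FAS) comprises all subjects to whom study treatment has been assigned by randomization". The other follows dosing: "The Safety Set (SAF) includes all subjects who received at least one dose of study treatment". For the primary endpoint, section 2.5.1 says "Analysis of the primary endpoint will utilize the FAS", and its first ground for non-response is that "a subject does not complete one year on the initially assigned treatment or" (the list then continues).

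Section 2.5.4 adds three COVID-19 supplementary items. Item b is the estimand, and its aim is to "estimate the treatment effect had COVID-19 pandemic not occurred". It keeps the composite responder definition, the CMH odds ratio, and non-responder status for discontinuation unrelated to COVID-19. For COVID-related discontinuation of the initial treatment it uses a hypothetical strategy: later MMD data are ignored and imputed to week 52 under MAR. Its population, however, is this: "The target population is defined by all subjects in the study who received at least one dose of study treatment". That is the Safety Set criterion, and no reason is given for it.

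The SAP foresees subjects who never start. Section 2.1.1.3 states: "For subjects who are randomized but not dosed after randomization, the Study Day 1 is defined as the date of randomization".

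**The concern.** An analysis meant to show the effect without the pandemic is read beside the primary result. It can be read that way only if the two differ solely in how pandemic-related events are treated. Item b changes two things at once: the handling of COVID-related discontinuation, and who is in the denominator.

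The second change conditions on something that happens after allocation. The trial is open-label (protocol 6.4), so whether a subject starts the allocated drug can depend on knowing what it is. Dropping those who do not start gives up part of the protection that randomisation provides.

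The restriction can also remove subjects whom the estimand is meant to address. SAP 2.3.2 lists treatment not given among its COVID-19 deviations. A subject who never started because of the pandemic is a pandemic-affected non-responder in the primary analysis, yet item b drops that subject and applies no hypothetical strategy.

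**Working it through.** **1. Inputs.** SAP section 3 and protocol 12.8.1 give a control rate of 0.18, an odds ratio of 2, 2:1 allocation, 394 erenumab and 197 control subjects, two-sided alpha 0.05 and 90% power. The erenumab rate follows: odds = 2 × 0.18/0.82 = 0.4390, so the rate is 0.4390/1.4390 = 0.3051. The difference is 0.125, against a stated 12%.

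**2. The plan's own figure.** The stated total is 591. A two-proportion formula with continuity correction gives 198 control subjects and 594 in total. A two-stratum CMH power formula (70/30 split, same control rate in both strata, continuity-corrected) gives 592. Power at 394:197 is 0.900 with the correction and 0.917 without it. The plan's figure reproduces, so the planning rates are a fair base for what follows.

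**3. Effect of the population change alone.** Treat the planning rates as FAS rates. Let u be the share of an arm that is never dosed. All of these subjects are FAS non-responders, so removing them changes the arm's rate from p to p/(1 − u) and its odds to p/(1 − u − p). No COVID-19 event is handled anywhere in this step. The documents give no value for u, so every row below except the first is an assumption.

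| Never dosed, erenumab | Never dosed, control | Erenumab rate | Control rate | Odds ratio |
|---|---|---|---|---|
| 0% | 0% | 0.3051 | 0.1800 | 2.000 |
| 1% | 1% | 0.3082 | 0.1818 | 2.004 |
| 2% | 2% | 0.3113 | 0.1837 | 2.009 |
| 5% | 5% | 0.3211 | 0.1895 | 2.024 |
| 0% | 2% | 0.3051 | 0.1837 | 1.951 |
| 0% | 5% | 0.3051 | 0.1895 | 1.878 |
| 2% | 0% | 0.3113 | 0.1800 | 2.059 |
| 5% | 0% | 0.3211 | 0.1800 | 2.155 |

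Example, 5% in control only: control odds = 0.18/(1 − 0.05 − 0.18) = 0.18/0.77 = 0.2338; odds ratio = 0.4390/0.2338 = 1.878. In subjects, 5% of control is about 10 of 197, and 5% of erenumab is about 20 of 394.

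**4. Scale.** The standard error of the log odds ratio at the planned size is √[1/(394 × 0.3051 × 0.6949) + 1/(197 × 0.18 × 0.82)] = √(0.0120 + 0.0344) = 0.215. The approximate 95% interval around 2.00 is therefore 1.31 to 3.05. The shifts in the table are small beside sampling error. The two analyses share almost all their subjects, though, so the difference between them is less noisy than either result.

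**5. Who exactly is excluded.** SAP 2.1.1.1 takes study treatment to be the drug assigned at randomisation. The Safety Set rule in 2.2 also admits the first treatment received when the assigned one never was. Section 2.1.1.3 has a separate rule "for subjects who are randomized but not dosed during initially assigned treatment period", which goes on to cover those dosed only after switching. Those subjects leave item b under the first meaning and stay under the second. The clear case for exclusion is the subject who received nothing at all.

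**The case against.** The best case for leaving item b alone is that it may not matter. A date rule for undosed subjects is standard SAP drafting and says nothing about how many there are. Randomisation takes place at the Day 1 treatment visit, where study drug administration is also scheduled (protocol 6.3.2 and Table 8-1), so there is little time in which to drop out before a first erenumab dose. If the number is zero the sets coincide, and if it is small and balanced the effect is negligible. Any gap would be visible, because SAP 2.3.1 tabulates the number of subjects in each analysis set. Item b is supplementary, and protocol 12.4.4 leaves such analyses to the SAP. All of this stands. It limits the size of the point but gives no reason for the restriction.

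A reader might infer that never-dosed subjects will be concentrated in the oral arm, because erenumab is injected by site staff (protocol 6.6.1) while oral drugs are sourced locally (protocol 6.7.1.1). That is plausible, but neither document states it. A reader might also infer a bias in favour of erenumab. The arithmetic does not support that: losing undosed control subjects lowers the odds ratio, losing undosed erenumab subjects raises it, and the documents do not say which would dominate.

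A further objection is that changing the population would not by itself make item b answer its question. Its responder rule still requires a completed year on the initial treatment. Read literally, someone who stopped because of COVID-19 fails that condition whatever MMD is imputed. This is correct, and the fix has to cover it.

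**Conclusion.** The mismatch is real and can be seen by reading the SAP against itself: item b's population differs from that of the primary analysis it is meant to illuminate, without explanation. The consequence is conditional. If some randomised subjects were never dosed, a difference between the item b and primary odds ratios cannot be attributed to the COVID-19 handling alone, and the randomised comparison is not fully preserved. It would go too far to say that item b necessarily fails to isolate the pandemic effect through its population.

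With up to 5% undosed in one arm only, the planning odds ratio moves to somewhere between 1.88 and 2.16. With equal shares up to 5%, it moves by at most about 0.02. These figures rest on assumed shares, on the planning rates holding in the FAS, and on the same rates in both strata. The primary FAS result, its test and the sample size are untouched. The point is minor and worth correcting because the correction is cheap.

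**What to change.** Amend item b of SAP 2.5.4 as follows:

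- Define the target population as the FAS.
- Count subjects never dosed for reasons unrelated to COVID-19 as non-responders, as in the primary analysis.
- Handle subjects never dosed for COVID-related reasons under the same hypothetical MAR strategy as COVID-related discontinuations. They have no on-treatment MMD, so imputation rests on treatment arm, baseline MMD and the baseline covariates already listed in SAP 5.1.4.3.2.
- Reword the responder rule so that COVID-related discontinuers are classified from imputed MMD and do not fail the completion condition automatically. State the assumption this makes, namely that they would otherwise have completed the year.
- If a dosed-only version is wanted, keep it as a separately labelled analysis and say whether a first dose taken only after switching qualifies.

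The cost is a few sentences in the SAP and a small programming change. No new data are needed, and the primary analysis does not change.
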